## 20. DATA COLLECTION

Data collection will take place in the immediate period after the kidney transplant in recovery, at 24, 48, and 72 hours postoperatively in the ward and at the three-monthly postoperative clinic visit.

The data will be collected prospectively and independently for both groups over a two-year period. Data collection may culminate earlier if the required sample size is achieved. It will include participant's demographic characteristics and the outcomes that will be measured to achieve the respective objectives of the study.

The outcomes will be measured to achieve the objectives of the study.

### 20.1. PARTICIPANT'S DEMOGRAPHIC CHARACTERISTICS

- a. Age at the time of operation in years and months (not the date of birth), gender, and BMI.
- b. Cause of renal deterioration.
- c. Dialysis modality at the time of transplantation
- d. Time on the kidney transplant waiting list
- e. Source of the donated kidney (living versus deceased donor)
- f. Prior renal transplant
- g. Surgeon undertaking the procedure (coded to maintain anonymity)
- h. Recipient risk factors for transplant surgery (age > 70 years, BMI > 30, cardiovascular disease, smoking, peripheral vascular disease, thromboembolic disease, hypertension (HTN), diabetes mellitus (DM), and urological obstructive symptoms)
- i. Donor risk factors for transplant surgery (Donor age > 60 years, BMI > 30, cardiovascular disease, smoking, peripheral vascular disease, hypertension (HTN), diabetes mellitus (DM), cold ischemia time (CIT), cause of death, HLA mismatch, and the number of vessels on the graft).

**20.2. OUTCOME MEASURES FOR OBJECTIVE 1:** To assess the capability of vascular monitoring device in the early postoperative care of kidney transplant patients.

- a) The number of early vascular complications identified and their management (incidence).
- b) The period between the graft implantation and diagnosis of vascular complication (early or late).
- c) The number of departmental ultrasound scans requested by the clinicians taking care of the patients in the first 24, 48, and 72 hours postoperatively.
- d) The 03-month kidney graft survival (the number of grafts lost due to vascular complications in the first 03 months).

**20.3. OUTCOME MEASURES FOR OBJECTIVE 2:** To assess the research methods used to compare vascular monitoring device with the standard care and to estimate surgical outcome measures essential to inform the sample size calculation for the definitive planned RCT.

- a. Suitability of eligibility criteria and recruitment process.
- b. Refusal rates for participation and randomization
- c. Retention and follow-up rates during the research process

- d. Assessment of the study methods, procedures, and follow-up schedules (researcher and participants)
- e. Assessment of the procedures for monitoring variation and fidelity in the delivery of the intervention. A fidelity checklist will evaluate the adherence to the standardised protocol of intervention delivery (i.e. consent of the participants, delivery of the intervention, and conduct of the serial Doppler signal monitoring).
- f. Assessment of the feasibility, appropriateness and performance of the potential outcome measures for the definitive multi-centre RCT.
- g. Calculation of the means and standard deviation of the outcome measures arising from the differences between the intervention and control arm essential to inform sample size calculation for the definitive planned RCT.

**20.4. OUTCOME MEASURES FOR OBJECTIVE 3:** To assess the availability of research resources, management support, potential barriers, and challenges for the definitive planned RCT.

- a) Assessment of ease and simplicity of the participant documentation (i.e. participant information sheet, consent form, data collection sheet) through the study
- b) Availability of equipment and medical staff in the host centre to handle the number of participants and the research procedures
- c) Technological capacity for communication and adequate software to randomize, record, process, and store research data.
- d) Availability of management support for the research project and back up plans for any extenuating circumstances.
- e) Documentation of any technical glitches or postoperative complications related to application of the monitoring device.
- f) To explore factors that will enable future economic evaluation of the vascular monitoring device in the definitive planned RCT (i.e., testing procedures that can collect information to inform a cost effectiveness analysis).

Data will be collected by the chief investigator using a standardised proforma in the Microsoft Office Excel Database (Microsoft Corporation, San Jose CA, USA). All collected data will be pseudonymised using unique anonymised codes. It will be kept strictly confidential and will not contain any participant identifiers.

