Exclusion criteria	
 
• Patients who will have a kidney transplant with more than two arteries (evident at the time of surgery).
 
• Patients below 18 years of age.
 
• Patients lacking capacity or unwilling to give consent.
 

Embedded qualitative study	Using the phenomenology approach, semi-structured interviews with open-ended questions will be conducted with the stakeholders (clinicians, nurses, and kidney transplant patients) directly involved with the implantable vascular monitoring device (n=12). The interviews will be aimed at exploring the experiences of participants (receiving/delivering the intervention) and suggestions of the stakeholders on participating in the study.
Study duration	24 months
Follow up for assessment of outcomes	
 
• In the immediate period after the kidney transplant in recovery,
 
• At 24, 48, and 72 hours postoperatively in the ward
 
• At the three-monthly postoperative clinic visit.
 

Trial Arms	
a) Intervention group: kidney transplant patients with the vascular monitoring device):
 
The kidney transplant patients will receive the Implantable continuous vascular monitoring device surveillance for the first 72 hours in addition to the standard care clinical observation as part of their postoperative care.
 
b) Control group (kidney transplant patients with standard care clinical observation)):
 
The kidney transplant patients will receive the standard care clinical observation as part of their postoperative care.

The Outcomes that will be measured to achieve objectives (1-4)	
Objective 1: To assess the capability of vascular monitoring device in the early postoperative care of kidney transplant patients.	
 
a. The number of early vascular complications identified (incidence).
 
b. The period between the graft implantation and diagnosis of vascular complication (early or late).
 
c. The number of departmental ultrasound scans requested in the first 24, 48, and 72 hours postoperatively.
 
d. The 03-month kidney graft survival
 

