### 6.2. PROBLEM OF EARLY GRAFT LOSS (EGL)

About 7-10% of the transplanted kidneys are lost to complications in the first three months after transplantation and is termed as early graft loss (EGL). Vascular complications are one of the contributing factors accounting for 30-35% of EGL . Other studies have reported that vascular complications result in 20% of the total kidney grafts lost during the first 30 days after implantation .

[figure not shown]
EGL is a medical catastrophe in kidney transplant recipients with 30-day and 90-day mortality rates of 5.2% and 11.1% respectively . Other studies have reported an increase of 12.28% in the first-year mortality of kidney transplant recipients that suffer EGL. This is due to the physiological stress of returning to dialysis, cardiovascular complications, infections, and morbidity encountered for the removal of the failed graft . Also, EGL is an emotionally devastating outcome for both the patients and the transplant team . About 20% of the National kidney transplant waiting list compromise of the patients that have fallen back after graft loss and activated for re-transplantation that leads to a burden on the limited pool of suitable donor organs . This cascade of complex repercussions also decreases the survival of the patients already present on the transplant waiting list (TWL) who are running out of their dialysis options by increasing the waiting time .

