### Data Collection (Measures, Time-points and Location)

Measures	Time- Points				
	Immediate Postop	At 24 hours Postop	At 48 hours Postop	At 72 hours Postop	At 03 Months Postop
1. Quantitative Study					
a. The number of early vascular complications identified (incidence).	X	X	X	X	
b. The period between the graft implantation and diagnosis of vascular complication (early or late).	X	X	X	X	
c. The number of departmental ultrasound scans requested in the first 24, 48, and 72 hours postoperatively.	X	X	X	X	
d. The 03-month kidney graft survival					X
2. Qualitative Study					
Exploring the views of stake holders regarding				X	
a. Experience with the intervention				X	
b. participating in the study, and				X	
c. acquiring their suggestions to improve the design of definitive future RCT				X	
Location	Operation theatre recovery	Ward	Ward	Ward	Clinic

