## 22. DATA ANALYSIS

It is inappropriate to use inferential statistics in feasibility study data to formally test the effectiveness of an intervention. Data analyses using descriptive statistics will be performed in IBM SPSS version 25.0. The means and standard deviations will be

considered as the representative value of the continuous variables (i.e. participant's demographic characteristics) . The categorical variables (i.e. surgical outcomes) will be expressed by frequency distributions (percentages) and elaborated using tables and graphs .

The outcomes for each objective in both groups (i.e. intervention and control) will be summarised using descriptive statistics. The numerical data from both groups will be compared to describe the feasibility of the intervention and generate realistic estimates of important parameters for the definitive multi-centre RCT.

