### **22.1. PARTICIPANT'S DEMOGRAPHIC CHARACTERISTICS**

The participant's demographic or baseline characteristics in both groups will be summarised separately using descriptive statistics. The numerical data for both groups will be compared in the tabular form to demonstrate whether or whether not the participant's baseline characteristics in the Intervention and Control groups are identical.

**22.2. OUTCOME MEASURES FOR OBJECTIVE 1:** To assess the capability of vascular monitoring device in the early postoperative care of kidney transplant patients.

The first step will be to evaluate if the vascular monitoring device truly works in the sense of achieving its intended outcome (i.e. vascular monitoring in kidney transplant patients). According to the MRC Framework assessing a clear theoretical basis for the intervention is paramount for further evaluation of complex interventions . The percentages of the surgical outcomes in the Intervention and Control groups will be compared in tabular form. From this comparison, it will be noted whether the vascular monitoring device can safely identify vascular complications and prevent graft loss.

The relative risk or risk ratio for the surgical outcomes will also be calculated using the following formula.

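### The outcome called three-month graft survival (20.2 d) counts only grafts lost to vascular complications, and no by-arm line for loss from any cause is defined

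*Protocol*

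**What the plan says.** Section 20.2, item d, of the protocol gives the only definition of this outcome: "The 03-month kidney graft survival (the number of grafts lost due to vascular complications in the first 03 months". The study summary (section 4) lists it as "The 03-month kidney graft survival", and the data collection table schedules "d. The 03-month kidney graft survival" at three months. Neither states a cause or a definition. The document supplied as the SAP is a data management plan and defines no outcomes.

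The background in section 6.2 treats early graft loss more broadly: "About 7-10% of the transplanted kidneys are lost to complications in the first three months after transplantation". It then says "Vascular complications are one of the contributing factors accounting for 30-35% of EGL".

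Two uses of the outcome are planned:

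- Section 22.2 compares outcome percentages by arm, with a risk ratio and a risk difference, and says "it will be noted whether the vascular monitoring device can safely identify vascular complications and prevent graft loss".
- Section 20.3 g asks for summary statistics of "outcome measures arising from the differences between the intervention and control arm essential to inform sample size calculation for the definitive planned RCT", and section 22 says the by-arm comparison will "generate realistic estimates of important parameters for the definitive multi-centre RCT".

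**The concern.** Graft survival ordinarily means that the graft is still working, whatever might have ended it. Item d counts only failures attributed to vascular complications, so it is neither graft survival nor early graft loss as section 6.2 uses that term. A graft lost for another reason would not be an event.

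Three things are at stake.

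- **The reported figure.** Published under the survival label, it would look better than the true graft survival.
- **The conclusion in section 22.2.** It is not limited to vascular loss, and a vascular-only count cannot by itself support it.
- **The definitive trial.** A vascular-loss rate mistaken for a graft-loss rate would be about one third of the right size.

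Item d also requires someone to judge whether a loss was vascular, and section 19 says that clinicians and data collectors cannot be blinded. A line for loss from any cause does not depend on that judgement.

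**Working it through.** The plan has no figure to reproduce. Section 15 sets 50 patients on practical grounds, with no power calculation and no expected event count.

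**Inputs**
- 50 patients, 25 per arm (section 15).
- Three-month graft loss E = 7% to 10% (section 6.2).
- Vascular share of that loss s = 30% to 35% (section 6.2).

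The rates are literature figures, applied here to both arms alike.

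**Share of losses that are not item d events**

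1 − s = 1 − 0.35 = 65% to 1 − 0.30 = 70%.

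Section 6.2 also gives a vascular share of 20%, but for the first 30 days. It would make the share 80% and is not used here because the window differs.

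**Expected counts**

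| Quantity | Formula | Low | High |
|---|---|---|---|
| All losses, 50 patients | 50 × E | 50 × 0.07 = 3.5 | 50 × 0.10 = 5 |
| All losses, per arm | 25 × E | 1.75 | 2.5 |
| Vascular-loss risk | E × s | 0.07 × 0.30 = 2.1% | 0.10 × 0.35 = 3.5% |
| Item d events, 50 patients | 50 × E × s | 1.05 | 1.75 |
| Item d events, per arm | 25 × E × s | 0.53 | 0.88 |
| Losses outside item d, 50 patients | 50 × E × (1 − s) | 50 × 0.07 × 0.65 = 2.3 | 50 × 0.10 × 0.70 = 3.5 |

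**What would be reported as survival**
- From item d: 1 − 0.035 = 96.5% to 1 − 0.021 = 97.9%.
- Counting every loss: 1 − 0.10 = 90% to 1 − 0.07 = 93%.

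**Chance that an arm of 25 shows no event**
- Item d: (1 − 0.035)^25 = 41% to (1 − 0.021)^25 = 59%.
- Any cause: (1 − 0.10)^25 = 7% to (1 − 0.07)^25 = 16%.

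**Illustration for the definitive trial**

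The documents give no effect size, power or significance level for that trial. Assume that the device halves vascular loss and changes nothing else, with 80% power and a two-sided 5% test of two proportions (pooled variance under the null). The absolute difference, E × s / 2, is then the same for both outcomes, but the background rate is not.

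| E | s | Vascular loss, control v device | n per arm | Any-cause loss, control v device | n per arm | Ratio |
|---|---|---|---|---|---|---|
| 7% | 30% | 2.1% v 1.05% | 2,207 | 7% v 5.95% | 8,622 | 3.91 |
| 7% | 35% | 2.45% v 1.225% | 1,886 | 7% v 5.775% | 6,254 | 3.32 |
| 10% | 30% | 3% v 1.5% | 1,534 | 10% v 8.5% | 5,856 | 3.82 |
| 10% | 35% | 3.5% v 1.75% | 1,310 | 10% v 8.25% | 4,250 | 3.24 |

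The two outcomes imply trials that differ in size by a factor of 3.2 to 3.9.

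**The case against.** The strongest reply is that a vascular-loss count is the right outcome for a vascular monitor. Section 18.1 sets out the mechanism: complications found sooner, corrected sooner, fewer grafts lost. Read in that light, the sentence in section 22.2 is about vascular loss and is only loosely worded. The restriction is printed in brackets straight after the label, so anyone who uses item d can see what it counts.

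The data are probably not lost either. A graft loss would ordinarily meet the serious adverse event definition (37.1.3), all adverse events go on the case report form (37.2), and section 21 says data will be summarised by group. No hypothesis test is planned. The documents do not say that item d will size the definitive trial, and 20.3 f leaves the choice of outcome open. The background rates may not transfer to this centre.

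Part of this stands. The vascular count is worth keeping, the gap lies in definition and planned reporting rather than in data capture, and the sample-size comparison is only an illustration.

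The rest does not remove the defect. The bracketed text is itself the mismatch with the label. Section 21 is general and names no line for loss from any cause, and section 22 plans no by-arm summary of adverse events. If the summary and the data collection table mean ordinary graft survival, they contradict 20.2 d. If they are short forms of it, no outcome for loss from any cause exists. Assessing candidate outcome measures and passing on their estimates are stated aims of this trial, so an outcome open to two meanings matters even without a test.

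**Conclusion.** The point holds and should be fixed. Followed as written, 20.2 d would report under the name of graft survival a figure that leaves out about 65-70% of three-month losses: about 96.5-97.9% instead of 90-93%. The event rate would be 2.1-3.5% instead of 7-10% if it were taken for all graft loss. The count cannot by itself support the unrestricted statement in section 22.2.

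The sizes rest on the literature rates in section 6.2 holding in both arms, and that section does not say whether death with a functioning graft is within the 7-10%. The mismatch between label and definition depends on no rate. This trial has no power or error rate that could be affected.

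**What to change.** Report two lines by randomised arm:

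1. Three-month graft survival, counting loss from any cause and stating how death with a functioning graft is counted.
2. The number of grafts lost to vascular complications by three months, labelled as such.

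Use the same wording in the study summary, 20.2 d and the data collection table. Tie the statement in section 22.2 to the line that supports it, and say under 20.3 g which line is carried forward to the definitive trial.

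The cost is one definition and one extra table row. The three-month clinic visit is already scheduled (section 20), and the medical notes and renal database are already accessed (section 35). The downside is that the survival figure will be less favourable and less specific to the device. It will also stay imprecise at 25 per arm: with 2 losses in 25 (8%), the exact (Clopper-Pearson) 95% interval runs from about 1% to 26%.

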#### **6.4. KNOWLEDGE GAP IN EGL:**

Presently the clinicians caring for the transplant recipients postoperatively manage them by the standard care clinical observation. They keep a low threshold for requesting departmental ultrasound scans even for a minimal clinical suspicion of graft hypoperfusion however, there is a tendency to miss cases. A departmental ultrasound scan is a non-invasive radiological investigation that detects vascular complications with a sensitivity of 97%. Nevertheless, this investigation has limitations. It is operator-dependent, has patient limitations if the patient has a high BMI or is uncomfortable due to postoperative pain, takes time to be organised and multiple serial scans are required for continuous monitoring which can be administratively difficult.

Although not widely used in transplant units across the UK, the implantable continuous vascular monitoring device has been used intermittently in our kidney transplant centre for the last nine years. We availed of this opportunity and conducted a service evaluation by undertaking a retrospective evaluation of the prospectively maintained medical notes to describe and compare clinical outcomes in all patients who underwent kidney transplant surgery at our unit with and without this monitoring device. Despite the methodological limitations, the results of this study were suggestive of the usefulness of the monitoring device.

There is a clinical requirement for a reliable continuous vascular monitoring mechanism in kidney transplant surgery. The literature revealed a lack of information and gaps in the evidence on the possible role of a continuous vascular monitoring device in kidney transplantation. Therefore, we propose feasibility RCT with an embedded qualitative study to inform the local practice and provide preliminary information for the definitive future RCT.

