## **15. SAMPLE SIZE**

This is feasibility RCT; it is not compulsory to perform a formal power calculation. The sample size is chosen based on the practicalities of conducting a feasibility study. The sample size is a realistic recruitment figure for 24 months based on a recent retrospective study conducted at the Southwest transplant centre leading to this research project. The data suggested that about 65-70 kidney transplants were performed annually in our unit. After exclusion criteria, we anticipate that about 100 patients will be available for recruitment in two-year study duration. The data also suggests that in the last five years there were minimal number of kidney transplant patients that opted not to receive additional vascular monitoring or refused participation after their procedure. This allows us the reassurance of minimum dropout rates in the study.

The COVID-19 pandemic has resulted in an unprecedented increase in our kidney transplant activity. It is due to the reason that the Southwest region has remained the least affected in the UK and our transplant centre remained open. On the contrary, most transplant units across the UK had to be closed down due to infection and resource constraints. This led to the increased

diversion of organ resources to the Southwest transplant centre. As a result, our End-stage renal disease (ESRD) patients availed themselves of the opportunity of more graft offers than usual. This allowed us to perform more transplant surgeries as compared to previous years.

The randomised controlled feasibility trial aims to recruit 50 kidney transplant patients within a 24-month period; 25 in intervention group and 25 in control group. In our study, we propose to attach an implantable continuous vascular monitoring device to half (i.e. 25) of the kidney transplant patients (intervention Group) during their surgery. Postoperatively, these patients will receive graft surveillance by the monitoring device in addition to the standard care clinical observation. The other half (i.e. 25) of the kidney transplant patients (control Group) will receive the standard care clinical observation.

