## 17. RANDOMISATION

The patients who consent to participate in the study will be randomised into two groups (i.e. intervention and control) by a secure online computer sequence generator system (<https://www.randomizer.org/#randomize>). Randomisation will be completed in a 1:1 ratio using random permuted blocks. Randomisation will be the responsibility of the delegated on-call Transplant Consultant.

The patients allotted to the Intervention group will have kidney transplants with the implantable continuous vascular monitoring device while those allotted to the Control group will have kidney transplants with standard care clinical observation (i.e. without implantable continuous vascular monitoring device). Following kidney transplant surgery, all patients will be managed in the standard way followed at the Southwest transplant centre as per the Trust protocol.

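### Objective 2(g) leaves the 25-versus-25 arm difference as the only named effect input to the definitive sample size, and that difference is too imprecise for the role

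*Protocol*

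**What the plan says.** Objective 2 (Protocol Sections 4 and 8.2) has two parts: to assess the research methods, and to estimate the surgical outcome measures needed to size a definitive RCT. Item (g) in Section 20.3, repeated in the Objective 2 row of Section 4, gives the deliverable: the "means and standard deviation of the outcome measures arising from the differences between the intervention and control arm essential to inform sample size calculation". Section 22 adds that figures from the two groups will be compared to "generate realistic estimates of important parameters for the definitive multi-centre RCT".

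Section 15 "aims to recruit 50 kidney transplant patients within a 24-month period; 25 in intervention group and 25 in control group", and gives practical recruitment as the reason for that number. Section 22 rules out inferential testing of effectiveness and plans descriptive statistics only. No minimum worthwhile difference, external effect estimate or confidence interval appears in the Protocol. The document supplied as the SAP is a data management plan and is silent on sizing.

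Section 6.2 gives the background rates: "About 7-10% of the transplanted kidneys are lost to complications in the first three months after transplantation", and "Vascular complications are one of the contributing factors accounting for 30-35% of EGL". Outcome (d) of Objective 1 counts grafts lost to vascular complications by three months.

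**The concern.** A sample size needs two kinds of input. Nuisance parameters, such as an SD or a control rate, have to be estimated. The target difference should be the smallest effect worth detecting. Item (g) asks for quantities arising from the arm differences, and nothing else in the plan fills the second slot. A reader who follows it will carry the observed difference forward as the planning effect.

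With 25 per arm and a rare event, that difference is mostly chance. A chance large difference leads to an underpowered definitive trial, and a chance nil or reversed one yields no sample size at all. Informing the definitive calculation is part of a headline objective, so the output should be usable.

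**Working it through.** There is no calculated figure to reproduce: 50 is a recruitment target with no alpha, power or effect behind it.

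**Inputs from the Protocol.** 25 per arm (Section 15); 1:1 allocation (Section 17); all-cause early loss 7–10%, with a vascular share of 30–35% (Section 6.2). Implied vascular graft loss: 0.07 × 0.30 = 2.1% to 0.10 × 0.35 = 3.5%.

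**Assumptions, not in the documents.** Two-sided 5%, 80% power, no dropout, and the true effects shown below.

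**Expected events under a halving.** Controls: 25 × 0.021 = 0.53 to 25 × 0.035 = 0.88. Device arm: 0.26 to 0.44.

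**Sample size per arm** (two proportions, pooled variance under the null):

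N = [1.960·√(2p̄(1−p̄)) + 0.842·√(p₁(1−p₁) + p₂(1−p₂))]² / (p₁−p₂)²

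- True need, 3.5% v 1.75%: (0.443 + 0.190)² / 0.0175² gives 1,310.
- True need, 2.1% v 1.05%: 2,207.
- Implied by an observed 1 v 0 (4% v 0%): (0.388 + 0.165)² / 0.04² gives 192.
- Implied by 2 v 0: 93. By 2 v 1: 553. By 3 v 1: 180.

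The commonest non-tied result, 1 v 0, is therefore 1,310/192 ≈ 7 to 2,207/192 ≈ 11 times too small. A trial of 192 per arm would have 13–19% power for the halving.

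**Exact enumeration.** Each pair of event counts (a control, b device) has probability Bin(a; 25, p₁) × Bin(b; 25, p₂). Each pair is classed as nil or reversed (b ≥ a), or by its implied N against the need.

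| True rates, control v device | Need per arm | Nil or reversed | N at most half the need | N above half and up to twice the need |
|---|---|---|---|---|
| Vascular loss 2.1% v 1.05% | 2,207 | 66% | 34% | <0.1% |
| Vascular loss 3.5% v 1.75% | 1,310 | 55% | 44% | 0.3% |
| Vascular loss 2.1% v 0% | 369 | 59% | 10% | 32% |
| Vascular loss 3.5% v 0% | 220 | 41% | 22% | 37% |
| All-cause loss 7% v 3.5% | 637 | 41% | 45% | 13% |
| All-cause loss 10% v 5% | 435 | 34% | 45% | 14% (a further 7% above twice) |

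Adding the two failure columns, before rounding, gives over 99% for halved vascular loss, 63–68% for abolished vascular loss and 80–87% for halved all-cause loss. With a 75% reduction in vascular loss the sum is 97–99%.

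Section 6.2 also reports that "vascular complications result in 20% of the total kidney grafts lost during the first 30 days after implantation". Applying that share to the three-month loss (an assumption) gives 0.20 × 7–10% = 1.4–2.0%, with fewer expected events still.

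**Continuous outcome, such as scan counts** (normal approximation, SD treated as known). The standard error of the standardised difference is √(2/25) = 0.283.

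- At a true 0.3 SD the need is 2(1.960 + 0.842)²/0.3², or 175 per arm.
- The implied N is at most half the need when the observed difference is at least 0.3√2 = 0.424. That probability is 1 − Φ((0.424 − 0.3)/0.283) = 33%.
- The difference points the wrong way with probability Φ(−0.3/0.283) = 14%.
- The 33% falls to 23% at a true 0.5 SD and 12% at 0.8 SD.

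**What 50 patients can estimate.** The pooled SD on 48 degrees of freedom has 95% limits of 0.83 to 1.25 times the estimate, which is usable. A control event rate is not well estimated: 0/25 has an exact 95% upper limit of 13.7%, and 1/25 an interval of 0.1–20.4%.

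**The case against.** The strongest reply is that item (g) says the summaries will inform the calculation; it does not say the observed difference will be the target. Section 22 summarises each arm and speaks of parameters generally. Means and SDs by arm are legitimate inputs, and Section 22 reserves them for continuous variables, whereas the largest figures above concern a rare binary outcome. Item (f) exists to judge which outcomes suit the definitive trial, so this study might itself show that graft loss is unworkable.

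Much of this stands. The wording is loose rather than a stated wrong method, and the magnitude depends on the outcome and the assumed effect. It does not remove the point: the text ties the sizing input to arm differences, Objective 2 refers to surgical outcomes, and no alternative source for the effect is named.

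Several stronger readings are tempting but unsupported:

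- **Any sample size derived this way will be far too small.** This fails if the device abolishes vascular loss, and for most continuous-outcome scenarios.
- **A null difference would stop the definitive trial.** The Protocol has no such rule, and Section 25 expects to proceed to a multicentre RCT.
- **The primary outcome will be whichever difference looks largest.** Nothing proposes this.
- **Section 22 contradicts item (g).** It bars formal testing of effectiveness, not descriptive estimation.
- **The definitive trial would take an impossible number of years, judged by this trial's 25 patients a year.** Section 15 expects about 100 available patients in two years, and the definitive trial is to be multicentre.

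**Conclusion.** The point holds in a limited form and should be fixed. As written, the observed arm difference is the only effect input offered for the definitive sample size, and 25 per arm cannot supply one. For vascular graft loss at the implied 2.1–3.5%, under an assumed true halving with two-sided 5% and 80% power, well over 99% of such trials would give no sample size or one at most half the need. That falls to 80–87% for halved all-cause loss and 63–68% for abolished vascular loss. For a continuous outcome at a true 0.3 SD, 33% give at most half the need and 14% point the wrong way. The documents give no rate for early vascular complications, so no figure is offered for that outcome.

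A reader might infer that the feasibility trial itself is undermined. It is not: its conduct, data collection and descriptive analyses are unaffected, and harm arises only if a later protocol adopts the raw difference.

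**What to change.** Reword item (g) in Section 20.3 and its copy in Section 4, along these lines:

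*Means, SDs and event rates will be reported by arm with 95% confidence intervals. The pooled SD of ultrasound scan counts, together with recruitment, retention and fidelity, will inform the definitive sample size. The target difference will be a minimum worthwhile difference, stated with its rationale before outcomes are compared by arm. The observed difference between arms will not be used as the target.*

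Two details:

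- **SD.** Carry forward its confidence interval or an upper limit. An 80% upper limit is one convention: at 48 degrees of freedom it multiplies the variance, and so the sample size, by 1.21. This is a normal-theory figure and only approximate for skewed counts.
- **Control event rate.** Supplement the 25 controls with the unit's service evaluation, which set out to "compare clinical outcomes in all patients who underwent kidney transplant surgery at our unit with and without this monitoring device". Report its rate with an interval and state its limits. Section 6.4 gives no size and admits methodological limitations, and Section 28 says two of four surgeons used the device, so patients without it may be a selected group. It should supplement the trial's own rate, not replace it.

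The cost is protocol wording and one table from data the unit already holds, with no extra patients. The downside is that the definitive sample size may look less favourable.
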